6.21. Efficacy Assessments: Chronic Lymphocytic Leukemia

6.21.1. Tumor Status Assessments

The determination of CLL response and progression will be based on standardized IWCLL criteria {Hallek 2008}, as specifically modified for this study considering the pharmacology of GS-9973 and the methods to be used in evaluation. During the course of this study, investigators will periodically assess the status of each subject's CLL. If CLL progression is suspected, the IRC will be notified and radiographic and pertinent clinical data provided in order to provide expert interpretation (see Section 9.4). The findings of the IRC will be considered primary for analyses of PFS and other tumor control endpoints.

6.21.2. Method of Assessment

In addition to clinical examination, imaging-based evaluation will be used in this study in all subjects enrolled. CT scan is the preferred method for radiographic tumor assessment. MRI scanning may be used at the investigator's discretion in subjects for whom this may be a preferred alternative to CT scanning; however, if MRI is performed, a non-contrast CT of the chest should be performed. Contrast-enhanced scanning is preferred, but iodine-containing or gadolinium contrast material may be omitted in subjects for whom use of a contrast agent would be medically contraindicated. Chest x-ray, ultrasound, endoscopy, laparoscopy, radionuclide scans, or tumor markers will not be considered for response assessment.

At Screening CT or MRI of neck, chest, abdomen, and pelvis is required. At all timepoints after Screening imaging of the chest, abdomen, and pelvis will be required. Imaging of the neck is required at each follow-up time point if the neck scan was positive at baseline or if palpable neck lymphadenopathy appears during the course of the study.

For radiographic evaluations, the same method of assessment and the same technique (eg, scan type, scanner, subject position, dose of contrast, injection/scan interval) should be used to characterize each identified and reported lesion at baseline and during study treatment and follow-up. However, if a subject is imaged without contrast at baseline, subsequent assessments should be performed with contrast, unless the subject cannot tolerate the contrast. All relevant clinical and radiographic information required to make each tumor status assessment must be made available for source verification and for submission to the IRC (see Section 9.4).

6.21.3. Timing of Assessments

During screening, clinical and imaging-based tumor assessments should be performed within 5 weeks prior to the start of study drug. Clinical tumor assessments should be performed at each clinic visit. On-study CT/MRI tumor assessments should be performed at ~8- to 12-week intervals. An End of Study CT/MRI tumor assessment should be performed unless the subject already has radiographic confirmation of disease progression \leq 4 weeks prior to study drug discontinuation. If a subject permanently discontinues study drug prior to objective documentation of CLL progression, investigators should continue further follow-up at ~8 or ~12-week intervals until CLL progression is documented.

6.21.4. Identification and Follow-up of Tumor Lesions and Organomegaly

6.21.4.1. Index Lesions

At baseline, up to 6 lymph nodes should be selected as index lesions that will be used to quantitate the status of the disease during study treatment. Ideally, the index lesions should be located in disparate regions of the body. Only peripheral nodes need be selected as index lesions. However, it is optimal if mediastinal and retroperitoneal areas of disease are assessed whenever these sites are involved.

Index lesions will be measured and recorded at baseline and at the stipulated intervals during treatment. The cross-sectional dimensions (the largest cross-sectional diameter, ie, the LD \times the LPD will be recorded (in cm) for each index lesion. The product of the perpendicular diameters (PPD) for each index lesion and the SPD for all index lesions will be calculated and recorded. The baseline SPD will be used as references by which objective tumor response will be characterized during treatment. The nadir dimensions of individual lesions and the nadir SPD will be used as references by which CLL progression will be characterized. All LD and LPD diameters will be reported in centimeters and all PPD and SPD measurements will be reported in centimeters squared.

A nodal mass may be selected as a nodal index lesion if it is both abnormal and measurable at baseline. A lymph node lesion is considered abnormal if it has a single diameter that is >1.5 cm and is considered measurable if it has 2 perpendicular diameters that can be accurately measured in cross section with the LD being ≥ 1.0 cm and the LPD also being ≥ 1.0 cm.

At follow-up time points, the LDs for individual lesions and the SPD of all nodal index lesions will be considered. Because nodal index lesions that have one or both diameters > 0 cm and < 1.0 cm cannot be reliably measured, a default value of 1.0 cm will be assigned for each diameter that meets these criteria and the resulting PPD will be used in SPD calculations. Based on this convention, a CR may be achieved even if an SPD value is > 0 cm², (ie, if all lymph nodes measure < 1.0 cm²).

A new node that measures > 1.5 cm in the LD and > 1.0 cm in the LPD will be considered progressive disease.

In cases in which a large lymph node mass has split into multiple components, all subcomponents regardless of size will be used in calculating the SPD. Progression of the lesion will be based on the SPD of sub-components. Lesion sub-components will have the true PPDs calculated. Similarly, lesion sub-components that are visible but neither abnormal nor measurable will have the default PPD of 1.0 cm² (1.0 cm \times 1.0 cm) used in calculating the SPD.

If lesions merge, a boundary between the lesions will be established so the LD of each individual lesion can continue to be measured. If the lesions have merged in a way that they can no longer be separated by this boundary, the newly merged lesion will be measured bi-dimensionally.

6.21.4.2. Spleen and Liver

Both the spleen and liver should be assessed by CT/MRI scan at baseline and at the stipulated intervals during treatment. The baseline and nadir values for the longest vertical dimension (LVD) of each organ will be used as reference to further characterize the objective tumor response of the measurable dimensions of CLL during treatment. All spleen and liver LVD measurements should be recorded in centimeters.

6.21.4.2.1. Spleen

By imaging, the spleen will be considered enlarged if it is >12 cm in LVD {Bezerra 2005}, with the LVD being obtained by multiplying the number of sections on which the spleen is visualized by the thickness of the sections (eg, if the spleen is seen in 14 contiguous cross-sectional images with 0.5-cm thickness, the LVD is recorded as 7 cm).

For subjects with splenomegaly at baseline or at the splenic LVD nadir, respective response and progression evaluations of the spleen will consider only changes relative to the enlargement of the spleen (ie, the portion of the LVD that is >12 cm by imaging) at baseline or nadir, not changes relative to the total splenic LVD.

A 50% decrease (minimum 2 cm decrease) from baseline in the enlargement of the spleen in its LVD or decrease to ≤ 12 cm by imaging is required for declaration of a splenomegaly response. Conversely, an increase in splenic enlargement by $\geq 50\%$ from nadir (minimum increase of 2 cm) is required for declaration of splenic progression.

6.21.4.2.2. Liver

By imaging, the liver will be considered enlarged if it is >18 cm in LVD {Erturk 2006}.

A 50% decrease (minimum 2 cm decrease) from baseline in the enlargement of the liver in its LVD or decrease to ≤ 18 cm by imaging is required for declaration of a hepatomegaly response. Conversely, an increase in liver enlargement by $\geq 50\%$ from nadir (minimum increase of 2 cm) is required for declaration of hepatic progression.

6.21.4.3. Non-Index Lesions

Any other measurable and abnormal nodal lesions not selected for quantitation as index lesions may be considered non-index lesions. In addition, non-measurable evidence of CLL such as nodal lesions with both diameters < 1.0 cm, extra-nodal lesions, bone lesions, leptomeningeal disease, ascites, pleural or pericardial effusions, lymphangitis of the skin or lung, abdominal masses that are not confirmed and followed by imaging techniques, cystic lesions, previously irradiated lesions, lesions with artifacts may be considered as non-index disease.

The presence or absence of non-index disease should be recorded at baseline and at the stipulated intervals during treatment. If present at baseline, up to 6 non-index lesions should be recorded. The non-index disease at baseline will be used as a general reference to further characterize regression or progression of CLL during assessments of the objective tumor response during treatment. Measurements are not required and these lesions should be followed as “present”, unequivocally progressed or “absent”.

6.21.4.4. Biopsy

Biopsy is not required in the determination of subject eligibility. However, subjects with evidence of Richter's transformation to an aggressive lymphoma on biopsy are ineligible for study participation.

During study participation, a subject who has a biopsy indicating Richter's transformation to an aggressive lymphoma will be considered to have PD even in the absence of other evidence of PD. If the subject has no earlier objective documentation of PD, the date of the biopsy will be considered the date of CLL progression.

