For subjects with MCL, DLBCL, FL, CLL (except for the CLL dose ranging cohort), a Bayesian, continuous data review, which will be conducted independently, will be used to update the estimates of progression-free survival (PFS) rates at 16 weeks (CLL after BCR targeted therapy, MCL and DLBCL) or 24 weeks (CLL and FL), assessing the efficacy once each subject's primary endpoint becomes available for a cohort. Because it consists of 3 different histologies, accrual to the 'non-FL iNHL' cohort will continue to a maximum of 45 subjects without interim review. The continuous data review for MCL, DLBCL, FL and CLL cohorts (except for the CLL dose ranging cohort) will be conducted independently. Futility assessment will begin when the first eligible 10 subjects' primary endpoints become available.

Given the initial activity seen in the CLL cohort, which was treated with the original formulation, and improved PK of the new formulation, exploration of lower doses will be pursued in the 3 CLL cohorts {[Sharman 2015](#)}. Subjects who are treated at lower doses of GS-9973

SDD may have their dose escalated up to 400 mg (200 mg x 2) BID, if after 8 weeks there is less stable disease or at the time of disease progression, if the investigator feels it is in the subject's best interest.

Up to 40 subjects will be studied in each cohort of MCL, DLBCL, FL and CLL, up to 45 subjects will be enrolled in the non-FL iNHL cohort; up to 60 subjects will be enrolled in each cohort of CLL dose ranging, CLL prior BTK inhibitor exposure and CLL prior PI3K inhibitor exposure).

In the BCR targeted therapies cohorts, subjects who have progressed will be enrolled to either simple progression (Non-Richter's) or transformation (Richter's) to Richter's or Richter's-like disease. A biopsy is not required but encouraged if there is a clinical concern of possible transformation. In each BCR targeted therapies sub-cohort a) progression (Non- Richter's) or b) transformation (Richter's), a separate futility assessment will occur after the first 10 subjects are accrued in each sub-cohort. Thereafter, continuous data review may be conducted when a new primary endpoint becomes available.

- If the futility criterion is not met, subsequent subjects will be enrolled until a total number of 20 (Richter's) or 40 (Non-Richter's) subjects per cohort. The CLL subjects who were previously treated with BCR inhibitors will be recruited for a cohort dosed at 400 mg twice daily (BID) of GS-9973 SDD.

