3.1.1. CLL, FL, DLBCL, MCL

A Bayesian, continuous data review approach will be used to update the estimates of PFS rates at 16 weeks (CLL after BCR targeted therapy, MCL and DLBCL) or 24 weeks (CLL and iNHL) as each subject's primary endpoint becomes available for a malignancy. The criterion used for the futility boundary is defined as highly likely (>90%) that the PFS rates at 16 weeks (CLL after BCR targeted therapy, MCL and DLBCL) or 24 weeks (CLL and iNHL) are less than 0.2 given the available subjects' efficacy data.

Futility assessment begins when the first 10 subjects' primary endpoints become available. Thereafter, continuous data review will be conducted when a new primary endpoint becomes available.

- If the futility criterion is not met, subsequent subjects will be enrolled until a total of pre-defined number of subjects are recruited for a cohort.
- If the futility criterion is met, the sponsor will consider terminating enrollment to that malignancy, taking into account efficacy, drug exposure and subtype (for DLBCL), unless there are subjects who remain on treatment and have not yet reached 16 weeks (CLL after BCR targeted therapy, MCL and DLBCL) or 24 weeks (CLL and FL). In this case, enrollment will be suspended until the next on-going subjects' primary endpoint becomes available, and another data review is conducted. If, after review of all available subjects, the futility boundary has still been crossed and the lack of drug exposure or for DLBCL, subtype does not explain the lack of activity, enrollment to that malignancy will be terminated.

The futility boundary is provided in [Figure 3-2](#) with details in Section 8.6. The boundary is represented in terms of the total number of subjects and the number of progression-free subjects at Week 16 (CLL after BCR targeted therapy, MCL and DLBCL) or Week 24 (CLL and FL). Subjects who withdraw or are lost to follow-up before Week 16 (CLL after BCR targeted therapy, MCL and DLBCL) or week 24 (CLL and FL) will be considered as not achieving PFS for the analysis.

At each data review, if the observed ratio of the number of PFS at Week 16 (CLL after BCR targeted therapy, MCL and DLBCL) or Week 24 (CLL and FL) over the total number of subjects is at or below the futility boundary, then the futility criterion has been met.

The data review for the CLL prior BTK inhibitor exposure and CLL prior PI3K inhibitor exposure cohorts will be conducted independently for Richter's and non-Richter's.

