- c) The previously BCR treated patients will be limited to subjects with CLL (other BCR targeted therapies may be accepted after approval of the medical monitor) only in the context of this cohort are Richter's transformation eligible.
 - i) CLL subjects whom have had more than 1 BCR targeted therapy will be enrolled into the cohort of the most recent treatment ibrutinib or idelalisib received prior to progression.

- 5) Presence of radiographically measurable progressive disease as defined using Cheson criteria for NHL, and iNHL and by IWCLL criteria for CLL; lymphadenopathy or extranodal lymphoid malignancy (defined as the presence of ≥ 1 lesion that measures ≥ 2.0 cm in the longest diameter [LD] and ≥ 1.0 cm in the longest perpendicular diameter [LPD] as assessed by CT or MRI);
 - a) Subjects with LPL/WM who do not have radiographically measurable progressive disease must have a monoclonal serum IgM $\geq 2x$ ULN as verified by serum protein electrophoresis (SPEP) and with lymphoplasmacytic marrow involvement are eligible. LPL/WM enrollment is limited to those sites which have cryoglobulin analysis capabilities
- 6) All acute toxic effects of any prior antitumor therapy resolved to Grade ≤ 1 before the start of study drug (with the exception of alopecia [Grade 1 or 2 permitted], neurotoxicity [Grade 1 or 2 permitted], or bone marrow parameters [Grade 1, 2, or 3 permitted])
- 7) Karnofsky performance status of ≥ 60
- 8) Life expectancy of at least 3 months
- 9) Required screening laboratory data (within 5 weeks prior to administration of study drug) as shown in **Table 4-1**. *Note: Confirmation should be considered for out-of-range values to determine if the abnormality is real or artifactual. Values used for screening must be obtained within the screening period and should be the most recent measurement obtained. Subjects with any degree of neutropenia, thrombocytopenia, or anemia with documentation that it is due to malignancy may enroll.*

Table 4-1. Required Screening Laboratory Values

Organ System	Parameter	Required Value
Hematopoietic	ANC	$\geq 0.5 \times 10^9/L$
	Platelets	$\geq 50 \times 10^9/L$
	Hemoglobin	$\geq 80 \text{ g/L (8.0 g/dL)}$
Hepatic	Serum total bilirubin	$\leq 1.5 \times \text{ULN}$ (unless elevated due to Gilbert's syndrome or hemolysis)
	Serum ALT	$\leq 2.5 \times \text{ULN}$
	Serum AST	

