4.2.2. Exclusion Criteria

Subjects who meet any of the following exclusion criteria are not eligible for study participation:

- 1) Known histological transformation from iNHL or CLL to an aggressive form of NHL (ie, Richter transformation) if the CLL patient has not had ibrutinib or idelalisib as their immediately prior therapy. CLL patients who were treated with a BCR inhibitor as the most recent therapy and who experience a transformation of their tumor, will not be excluded. Subjects who have a history of iNHL or CLL with a subsequent confirmation high grade histology will be considered transformed for purpose of this study. *Note: Biopsy documentation of the absence or presence of transformation is not required*
- 2) Known active central nervous system or leptomeningeal lymphoma. *Note: Central nervous system imaging is only required in subjects with suspected lymphomatous involvement based on symptoms or signs*
- 3) Presence of known intermediate- or high-grade myelodysplastic syndrome (ie, subjects are excluded who have ≥ 5 bone marrow blasts; karyotypic abnormalities other than normal, Y deletion, 5q deletion, or 20q deletion; or ≥ 2 lineages of cytopenias) {Greenberg 1997}
- 4) Because they are likely to interfere with GS-9973 absorption, current therapy with agents that reduce gastric acidity, including but not limited to proton pump inhibitors
- 5) History of any prior lymphoid malignancy other than registration histology except for CLL subjects with prior BCR therapy
 - a) Subjects with diagnoses other than CLL who were previously treated with a BCR inhibitor are excluded from this study.

- 6) History of non-lymphoid malignancy except for the following: adequately treated local basal cell or squamous cell carcinoma of the skin, cervical carcinoma in situ, superficial bladder cancer, asymptomatic prostate cancer without known metastatic disease and with no requirement for therapy or requiring only hormonal therapy and with normal prostate-specific antigen for ≥ 1 year prior to start of study therapy, other adequately treated Stage 1 or 2 cancer currently in complete remission, or any other cancer that has been in complete remission for ≥ 5 years
- 7) Evidence of ongoing systemic bacterial, fungal, or viral infection at the time of start of study drug. **Note: Subjects with localized fungal infections of skin or nails are eligible.**

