6.21.5.4. Definitive Progressive Disease

The occurrence of any of the following events indicates definitive PD:

- Evidence of any new disease:
 - A new node that measures > 1.5 cm in the LD and > 1.0 cm in the LPD
 - New or recurrent splenomegaly, with a minimum LVD of 14 cm
 - New or recurrent hepatomegaly, with a minimum LVD of 20 cm
 - Unequivocal reappearance of an extra-nodal lesion that had resolved
 - A new unequivocal extra-nodal lesion of any size
 - New non-index disease unequivocally attributable to CLL (eg, soft tissue, effusions, ascites, or other organ abnormalities related to CLL)

Note: Isolated new effusions, ascites, or other organ abnormalities are not sufficient evidence alone of PD unless histologically confirmed. Thus, a declaration of PD should not be made if this is the only manifestation of apparently new disease.

- Evidence of worsening of index lesions, spleen or liver, or non-index disease:
 - Increase from the nadir by $\geq 50\%$ in the SPD of index lesions
 - Increase from the nadir by $\geq 50\%$ in the LD if an individual node or extra-nodal mass that now has an LD of > 1.5 cm and an LPD of > 1.0 cm
 - Splenic progression, defined as an increase in splenic enlargement by $\geq 50\%$ from nadir (with a minimum 2 cm increase and a minimum LVD of 12 cm)
 - Hepatic progression, defined as an increase in hepatic enlargement by $\geq 50\%$ from nadir (with a minimum 2 cm increase and minimum LVD of 18 cm)

- Unequivocal increase in the size of non-index disease (eg, effusions, ascites, or other organ abnormalities related to CLL)
- Transformation to a more aggressive histology (eg, Richter syndrome) as established by biopsy (with the date of the biopsy being considered the date of CLL progression if the subject has no earlier objective documentation of CLL progression).
- Decrease in platelet count or hemoglobin that is attributable to CLL, is not attributable to an autoimmune phenomenon, and is confirmed by bone marrow biopsy showing an infiltrate of clonal CLL cells
 - The current platelet count is $< 100 \times 10^9/L$ and there is a decrease by $> 50\%$ from the highest on-study platelet count
 - The current hemoglobin is $< 110 \text{ g/L (11.0 g/dL)}$ and there is a decrease by $> 20 \text{ g/L (2 g/dL)}$ from the highest on-study hemoglobin

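### Protocol 6.21.4.4 was not reconciled with the Richter's sub-cohorts: it calls biopsy-evident Richter's ineligible and, read literally, makes an on-study biopsy that only confirms the entry diagnosis a PFS event (minor)

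*Protocol*

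**What the plan says.** **Eligibility.** Protocol 6.21.4.4 states that "subjects with evidence of Richter's transformation to an aggressive lymphoma on biopsy are ineligible for study participation", without limiting this to any cohort. Inclusion criterion 4c (Protocol 4.2.1) says of the previously BCR-treated CLL subjects that "only in the context of this cohort are Richter's transformation eligible". Exclusion criterion 1 (Protocol 4.2.2) says that CLL patients whose most recent therapy was a BCR inhibitor and "who experience a transformation of their tumor, will not be excluded". The synopsis, Protocol 8.6 and Protocol 8.7 plan up to 20 Richter's subjects in each of the prior-BTK and prior-PI3K cohorts, with separate futility reviews. SAP Table 3-3 gives each Richter's group its own column.

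**Progression.** Under 6.21.4.4, during study participation "a subject who has a biopsy indicating Richter's transformation to an aggressive lymphoma will be considered to have PD". This applies even with no other sign of progression, and the event is dated at the biopsy unless progression was documented earlier. Protocol 6.21.5.4 lists as definitive PD: "Transformation to a more aggressive histology (eg, Richter syndrome) as established by biopsy". Neither section sets apart subjects who entered with Richter's. SAP 6.1.1 and Appendix 2 refer to Protocol 6.21 for CLL progression and add no exception.

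**Biopsy at entry.** It is not required. The synopsis says: "A biopsy is not required but encouraged if there is a clinical concern of possible transformation".

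**Futility looks.** After the first 10 subjects the synopsis says of the sub-cohorts that "continuous data review may be conducted when a new primary endpoint becomes available", whereas Protocol 3.1.1 says "continuous data review will be conducted when a new primary endpoint becomes available".

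**The concern.** Section 6.21.4.4 suits a CLL cohort from which transformed disease is excluded. It does not suit the BCR-exposed cohorts that were added later. The eligibility sentence conflicts directly with the current criteria.

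The progression sentence matters more for the analysis. Because histology is not required at entry, a subject can be classed as Richter's on clinical grounds and have a first confirming biopsy after dosing starts. Under the literal rule that biopsy is progression on its own date, although the disease state has not changed. The subject then fails the 16-week endpoint, both in the futility count and in the final Kaplan-Meier estimate. In a group of at most 20, a single such call can change the outcome of a look.

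**Working it through.** **Inputs.** Prior Beta(0.5, 1.5), futility if Pr(θ<0.2 | data) > 0.9, first look at 10 subjects, maximum 20 per Richter's sub-cohort (Protocol 3.1.1, 8.6, 8.7). With x progression-free subjects out of n, the posterior is Beta(x+0.5, n−x+1.5).

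**Plan's own figures.** At n=20 and an observed rate of 0.30 (x=6), the posterior mean is 6.5/22 = 0.295 with 95% interval (0.129, 0.497), as in Table 8-2. All seven rows of that table reproduce. An exact calculation with a look at every n from 10 to 40 gives futility probabilities of 0.837, 0.319, 0.072 and 0.0016 at true rates 0.1, 0.2, 0.3 and 0.5. Table 8-3 gives 0.8408, 0.3162, 0.0685 and 0.0015 from simulation, so the rule is being read as the plan intends.

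**Boundary up to n=20.** Futility is met at x=0 for n=10–13 and at x≤1 for n=14–20.

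| x/n | Pr(θ<0.2) | Result |
|---|---|---|
| 1/10 | 0.812 | continue |
| 0/10 | 0.975 | futility met |
| 1/11 | 0.845 | continue |
| 1/13 | 0.895 | continue |
| 1/14 | 0.913 | futility met |
| 2/14 | 0.726 | continue |

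**Effect of one miscall.** At n=20, 6/20 becomes 5/20. The observed rate falls from 30% to 25%, which is 5 points ignoring censoring, and the posterior mean falls from 0.295 to 5.5/22 = 0.250. At n=10, 1/10 becomes 0/10 and the look changes from continue to futility met. If the next subject succeeds, the count is 1/11 and the criterion is no longer met.

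**How often one miscall could decide the first look.** Exactly one success in 10 has probability 10 × 0.30 × 0.70⁹ = 12.1% at a true rate of 0.30, and 4.0% at 0.40. That single success must also be miscalled. At a true rate of 0.30 and assumed miscall rates m of 5% or 10%, the joint probability is 0.121 × 0.05 ≈ 0.6% or 0.121 × 0.10 ≈ 1.2%.

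**Crossing probability, illustrative.** The documents give no miscall rate. Let m be the assumed share of true successes miscalled, with none reversed, so the apparent rate is p(1−m). With the n=10 look alone, crossing is (1 − p(1−m))¹⁰; for example, p=0.30 and m=0.10 gives 0.73¹⁰ = 4.3%. With every look the exact recursion is used. Looks at n=10–19 suffice, because a crossing at n=20 implies one at n=19.

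| True rate | m | n=10 look only | Every look, n=10–19 |
|---|---|---|---|
| 0.30 | 0 | 2.8% | 5.7% |
| 0.30 | 5% | 3.5% | 7.1% |
| 0.30 | 10% | 4.3% | 8.8% |
| 0.40 | 0 | 0.6% | 1.1% |
| 0.40 | 5% | 0.8% | 1.6% |
| 0.40 | 10% | 1.2% | 2.2% |

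At a true rate of 0.30 the increase is 0.7 to 1.5 points with the first look alone and 1.4 to 3.1 points with every look.

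**Trigger.** Protocol Appendix 2 schedules no tumor biopsy for histology on study. The lymph node aspirates in Protocol 6.14 are for consenting subjects, at Cycle 1 Day 1 and at progression, for DNA and RNA analysis. The literal rule therefore needs an unscheduled biopsy.

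**The case against.** The eligibility sentence looks like an editorial leftover: the operative criteria, the futility rule, the sample size and the SAP tables all admit Richter's subjects. That is fair, and no effect on enrollment is shown. The contradiction still stands in current text.

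On progression, both 6.21.4.4 and 6.21.5.4 speak of transformation to something more aggressive, which most naturally means a change. A subject already transformed at entry has not changed. This is the sensible reading, but neither document states it, and a confirming biopsy also fits the words of 6.21.4.4.

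Other safeguards help in part:
- Primary PFS uses IRC findings, and investigator findings go only to a listing (SAP 6.1.1). The committee includes a hematologist or oncologist (Protocol 9.4), and SAP Appendix 2 says progression is to be identified from imaging and pertinent clinical data. The charter may already settle the matter, but it is not among the documents.
- The single-PD rule in SAP 6.1.1 could reverse an isolated call. It needs a later assessment, which is not assured because Protocol 5.6 ties definitive progression to withdrawal from treatment. In the protocol the rule appears in the NHL section, not in 6.21.5.4.
- Using the NHL criteria instead would not help, since Protocol 6.20.5.5 has parallel ineligibility and PD wording.
- Crossing the boundary leads the sponsor only to consider termination, and enrollment is suspended for a further review while subjects are pending (Protocol 8.6).

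The synopsis sentence encouraging biopsy follows the one on classifying subjects at enrollment, so it probably concerns entry. It does not show that on-study biopsies are expected.

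**Conclusion.** The point holds as a minor one. The text is wrong as written in two respects: the eligibility contradiction is plain, and the stated PD rule, followed literally and carried into the SAP, scores the entry condition of a planned sub-cohort as a primary-endpoint event.

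A reader might infer more than the documents support:
- **Richter's subjects fail the endpoint by design.** They do not. The rule covers biopsies during study participation, so a diagnostic biopsy before entry is not an event.
- **The 12.1% is a risk of wrongly meeting futility.** It is only the chance of exactly one success in 10. The chance that a miscall decides that look is about 0.6% to 1.2% at the assumed miscall rates.
- **Investigator and IRC readings could each drive the primary result.** Only the IRC reading does. What remains open is how the IRC treats such a biopsy.

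The size rests on an unknown frequency, which is probably low. The 0.7 to 3.1 point increase in crossing assumes a true rate of 0.30, miscall rates of 5% to 10%, no reversal, and crossing counted as the event.

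**What to change.** 1. Reconcile the ineligibility sentence in Protocol 6.21.4.4 with inclusion criterion 4c and exclusion criterion 1.
2. Reconcile the biopsy wording in Protocol 6.21.4.4 and 6.21.5.4 with the Richter's sub-cohorts. For the endpoint, state that histology which only confirms Richter's already classified at entry is not by itself a progression event.
3. Put that statement in Protocol 8.6, which governs the futility count, and in SAP 6.1.1 and Appendix 2, which govern final PFS. Put it also in the IRC instruction. A SAP edit alone would not reach the futility looks, because SAP 2.1 plans only a final analysis. Say how the statement relates to the single-PD rule.
4. Reconcile the result with the passages where progression bears on treatment (Protocol 5.6, 6.6 and 6.22), so that endpoint and treatment uses of PD do not drift apart. No treatment rule is proposed here.

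Subjects classed as non-Richter's at entry are unaffected. The cost is a protocol clarification, a few sentences in the SAP and one IRC instruction, with no new data.
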